8.4 REPORTING PROCEDURES

8.4.1 ADVERSE EVENT REPORTING

The sponsor-investigator must record non-serious adverse events and report to DSMC and IRB according to timetable for reporting specified in the Data Safety Monitoring Plan and per COMIRB's reporting requirements. Reporting will be done by the OCRST and [name].

8.4.2 UNANTICIPATED PROBLEM REPORTING

This study will follow COMIRB's guidance for UAP reporting and the DSMC's requirements (discussed below). AEs, noncompliance and protocol violations will be recorded and reported as required either promptly (within 5 days of Sponsor-Investigator's knowledge) or at the time of the study's continuing review.

It is the responsibility of the PI to report incidents or events that meet the criteria for UAPs reporting to their IRB using the IRB's standard UAP form. The PI is responsible for reporting the UAP to the UCCC DSMC, if applicable.

8.4.3 REPORTING OF PREGNANCY

This section is not applicable. Pregnancy will not affect the participant's eligibility or necessitate modification of study procedures.

8.5 SAFETY OVERSIGHT

The principal investigator will be responsible for the conduct of this study, overseeing participant safety, executing the data and safety monitoring (DSM) plan, and complying with all reporting requirements to local and federal authorities. This oversight will be accomplished through additional oversight from the Data and Safety Monitoring Committee (DSMC) at the University of Colorado Cancer Center (CU Cancer Center). The DSMC is responsible for ensuring data quality and study participant safety for all trials at the CU Cancer Center. A summary of the DSMC's activities is as follows:

- Conduct of internal audits

- Ongoing review of all serious adverse events (SAEs) and unanticipated problems (UAPs)
- May submit recommendations for corrective actions to the CU Cancer Center's Executive Committee

Per the CU Cancer Center Institutional DSM Plan, SAEs and UAPs are reported to the DSMC, IRB and the principal investigator per protocol. All SAEs and UAPs are to be reported to the DSMC within 7 (for fatal or life-threatening events) or 15 (non-life-threatening events) calendar days of the principal investigator receiving notification of the occurrence.

Study audits conducted by the DSMC will consist of a review of the regulatory documents, consent forms, and source data verification. Documentation of the audit conducted by the DSMC will then need to be submitted to the IRB of record at the time of the IRB's continuing review of this trial.

9 CLINICAL MONITORING

Clinical site monitoring will be conducted to ensure that the rights and well-being of human participants are protected, that the reported trial data are accurate, complete, and verifiable, and that the conduct of the trial is in compliance with the currently approved protocol/ amendment(s), with GCP, and with applicable regulatory requirement(s).

Monitoring for this study will be performed by CU Cancer Center Clinical Monitor in accordance with the clinical monitoring plan (CMP), incorporated herein by reference. The CMP describes in detail who will conduct the monitoring, at what frequency monitoring will be done, at what level of detail monitoring will be performed, and the distribution of the monitoring reports.

Independent audits will be conducted by the CU Cancer Center DSMC to ensure monitoring practices are performed consistently across all participating sites, if applicable, and that monitors are following the CMP.

10 STATISTICAL CONSIDERATIONS

10.1 STATISTICAL HYPOTHESES

- Primary Efficacy Endpoint(s):
Participants will find the intervention feasible and acceptable.
- Secondary Efficacy Endpoint(s):

(1) The HADS-A score will be smaller in patients receiving guided imagery intervention compared to controls (whose score should remain unchanged from baseline), and (2) the HADS-D score will be smaller in the guided imagery group compared to controls (whose HADS-D should increase over baseline)

10.2 ANALYSIS DATASETS

The dataset will consist of demographic and clinical information from the participant's medical chart. It will also include the self-reported data provided by study participants.

10.3 DESCRIPTION OF STATISTICAL METHODS

10.3.1 GENERAL APPROACH

Study Co-Investigator and biostatistician, [name], will conduct the analysis of the primary endpoint. [name] will conduct the analysis of the secondary endpoint using ATLAS.ti.

10.3.2 ANALYSIS OF THE PRIMARY EFFICACY ENDPOINT(S)

The purpose of the qualitative data analysis, which will address the secondary aim of this project, is an in-depth understanding of patient's acceptance and perceived usefulness of the guided imagery and music therapy interventions for addressing anxiety and distress related to radiation therapy. Analysis will begin with the transcription of each semi-structured interview into the coding software program. Qualitative analyses will be conducted using ATLAS.ti software, which will store, code, and categorize data transcripts. For this project, data will be analyzed with a constant comparative approach (39). This is an inductive approach to data analysis through which each piece of data (e.g., statements, emerging themes, etc.) is compared to other pieces of data and evaluated for similarities and/or differences. In qualitative research, it is generally accepted that data collection continues until "saturation" had been met. Saturation occurs once a researcher has collected enough case data that data provided by additional cases does not provide new information or themes. It has been suggested, from studies that utilize individualized interviews to develop and understand nuances of theory, that between 12-30 participants are typically needed to reach saturation (40).

10.3.3 ANALYSIS OF THE SECONDARY ENDPOINT(S)

The study investigators will use independent sample t-tests at the end of radiation treatment (RT) to test the hypotheses (1) the HADS-A score will be smaller in patients receiving guided imagery intervention compared to controls (whose score should remain unchanged from baseline), and (2) the HADS-D score will be smaller in the guided imagery group compared to controls (whose

HADS-D should increase over baseline). The study is powered to test these hypotheses. Additionally, we will analyze the data using repeated measures analyses or mixed models to study changes over time and to test for interactions between time and treatment groups.

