- **Primary Endpoint:**
Acceptability and feasibility of guided imagery intervention assessed through self-reported intervention use and qualitative interviews with intervention participants
- **Secondary Endpoints:**
Self-reported anxiety and depression at one month after completion of radiotherapy as measured by the Hospital Anxiety and Depression Scale
- **Tertiary/exploratory:**
Self-reported use of anxiolytic medications as measured by timeline follow-back methodology. We will also measure health-related quality of life in patients receiving the intervention and treatment as usual.

Population:

- **Sample size**
 - Maximum number of participants that can be enrolled is 72 (allow for screen failures)
 - Minimum number of participants to be enrolled 50 (number of participants needed to answer scientific question/aims)
- **Gender** Male and Female
- **Age Range** 18-100
- **Demographic group** Ambulatory outpatients receiving radiotherapy for head and neck cancer

- **General health status** Initiating radiotherapy for head and neck cancer

Number of Participating Sites enrolling participants:

[figure not shown]
1 (University of Colorado Cancer Center)

Description of Study

Agent: Guided imagery

Study Duration: 2 years

SCHEMATIC OF STUDY DESIGN

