4.2.3 EXPLORATORY ENDPOINTS

Participant use of anxiolytic medications will be assessed through both medical record review of prescriptions and patient reported use. All participants will record their use of any of the following medications: alprazolam, bromazepam, chlordiazepoxide, clonazepam, clorazepate, diazepam, flurazepam, and lorazepam. All participants will be given a TLFB measure to track daily use of anxiolytics during the course of the study. This will be administered weekly via a HIPAA secure REDCap link sent to his or her email. Participants who do not complete the weekly TLFB report in REDCap will be contacted by study staff in order to administer the recall via telephone. The TLFB is a reliable measure of patient-reported substance use (i.e., cigarettes, cannabis, and alcohol). Additionally, we will assess health related quality of life using the FACT-HN and symptom burden using the MSAS-SF. These measures will be included in exploratory analyses of the impact of the intervention on health-related quality of life and the impact of symptoms. Symptom presence may be included as a potential covariate in outcome analyses.

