7.3.2 ENROLLMENT/BASELINE

Enrollment: Day 1

Enrollment will generally occur on the same day as the Screening visit. However, interested patients can enroll in the study in the time between the Screening visit and CT simulation. There will be two possible routes for consent:

1. Participants may provide verbal consent for screening and baseline procedures only, and will provide a signed full consent prior to other study procedures (in person or via e-consent).
2. Informed consent and authorization for the entirety of the study will be obtained at the time of screening/baseline through an e-consent process. Signatures may be obtained via REDCap, mail, e-mail with scanned document or picture of the signed consent, or by bringing the signed consent and authorization into the clinic. All questions will be answered by the study personnel and/or treating physician

Study personnel will then complete the enrollment portion of the REDCap survey with the patient, which will include information regarding the patient's date of birth and email address. Additional information documenting the date of the informed consent as well as the consenting study personnel will also be collected.

The participant will complete study baseline measures and then will be randomized to either the intervention of treatment as usual condition. Participants may complete baseline measures any time after consenting and before the CT simulation visit.

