10.4 SAMPLE SIZE

We expect that we will be able to enroll up to 72 patients who will be randomized into either control (n=36) or guided imagery intervention (n=36). Based on a published study looking at HADS scores in HNC patients receiving RT (20), we used the values for means and standard deviations (SD) from that study for our control group. We also determined that SD would be known and equal. Significance levels (alpha) are set at 0.05 for a two-sided independent-sample equal-variance t-test. For the HADS-A hypothesis, the mean score in controls at the end of RT was 6.9 (SD = 5.0). With group sample sizes of 36 and 36, we will have 80% power to reject the null hypothesis of equal means when the HADS-A score in the guided imagery group is ≤ 3.6 (a $\geq 48\%$ difference between the scores for each group at the end of RT). For the HADS-D hypothesis, the mean score in controls at the end of RT was 11.2 (SD=5.5). Group sample sizes of 36 and 36 achieve 80% power to reject the null hypothesis of equal means when HADS-D score in the guided imagery group is ≤ 7.5 (a $\geq 33\%$ difference between the scores at the end of RT). Although we can achieve reasonable power to detect clinically significant differences

between our study groups, the main goal of this study is to determine the feasibility of a larger study. As such, the results of our analyses are not meant to answer the question of the effectiveness of our intervention, but to provide preliminary data for a larger grant application.

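### The powered HADS comparison ignores the baseline HADS score collected before randomisation and so gives up precision; the time point of an optional symptom covariate is left open.

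*Combined protocol and SAP*

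**What the plan says.** Section 10.3.3 sets out the HADS analysis: "The study investigators will use independent sample t-tests at the end of radiation treatment (RT) to test the hypotheses" on HADS-A and HADS-D, and adds that the study is powered for these hypotheses. Section 10.4 confirms the form of the test: "Significance levels (alpha) are set at 0.05 for a two-sided independent-sample equal-variance t-test". Neither section mentions a covariate.

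Section 10.3.3 then continues: "Additionally, we will analyze the data using repeated measures analyses or mixed models to study changes over time and to test for interactions". The interactions meant are those of arm with visit. It does not choose between the two kinds of model, and does not say whether baseline HADS is an outcome, a covariate or left out.

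Baseline HADS is available. Section 7.3.2 says "The participant will complete study baseline measures and then will be randomized", and both Table 2 and the schedule of events (7.4) list HADS-A and HADS-D at baseline and in Weeks 1, 3, 7 and 12. The hypotheses in section 10.1 are themselves framed against baseline: control HADS-A is expected to stay at its baseline level and control HADS-D to rise above it.

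The only covariate named anywhere is in section 4.2.3: "Symptom presence may be included as a potential covariate in outcome analyses". No time point is given. The MSAS-SF is scheduled at baseline and in Weeks 3, 7 and 12.

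**The concern.** A score measured before randomisation on the same scale as the outcome is usually the most useful covariate in a small trial. It cannot be affected by treatment, and it removes the part of the outcome variance that it predicts. The powered comparison leaves that variance in.

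Section 10.4 says the purpose of these analyses is "to provide preliminary data for a larger grant application". For that purpose the estimated difference and its interval matter more than the p-value, and an interval wider than necessary is less useful for planning the next trial. The loss matters most if enrolment ends near the minimum of 50 given in the Synopsis.

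The symptom covariate is a smaller, separate matter. Exploratory Aim 2 (section 2.2) hypothesises less symptom bother with guided imagery. If a symptom value from Week 3 or later were used and treatment had affected it, adjusting for it could remove part of the effect being estimated. The wording does not exclude this.

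**Working it through.** **Inputs from section 10.4.** Two-sided alpha 0.05; 36 per arm. HADS-A at end of RT: 6.9 in controls against 3.6, SD 5.0, difference 3.3. HADS-D: 11.2 against 7.5, SD 5.5, difference 3.7. From the Synopsis: minimum enrolment 50, taken here as 25 per arm.

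**Assumed input.** The correlation r between baseline and end-of-RT HADS is not in the documents. I used 0.3, 0.5 and 0.7.

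**Step 1: reproduce the plan's 80%.** SE = SD × √(2/n).
- HADS-A: 5.0 × √(2/36) = 1.179; 3.3/1.179 = 2.80; normal-approximation power Φ(2.80 − 1.96) = 80.0%. The noncentral t with 70 df gives 78.9%.
- HADS-D: 5.5 × √(2/36) = 1.296; 3.7/1.296 = 2.85; normal approximation 81.4%, noncentral t 80.4%.

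The stated 80% reproduces for both subscales. The figures below use the noncentral t.

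**Step 2: adjust for baseline.** The residual SD is SD × √(1 − r²), with 2n − 3 df. For HADS-A it is 4.77, 4.33 and 3.57 at r = 0.3, 0.5 and 0.7.

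| Power | Unadjusted | r = 0.3 | r = 0.5 | r = 0.7 |
|---|---|---|---|---|
| HADS-A, 36/arm | 78.9% | 82.5% | 89.0% | 97.2% |
| HADS-A, 25/arm | 62.8% | 66.9% | 75.2% | 89.3% |
| HADS-D, 36/arm | 80.4% | 83.9% | 90.1% | 97.6% |
| HADS-D, 25/arm | 64.5% | 68.5% | 76.7% | 90.4% |

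The half-width of the 95% confidence interval for HADS-A at 36 per arm is 1.994 × 1.179 = 2.35 points unadjusted, and 2.24, 2.04 and 1.68 adjusted. The difference detectable with 80% power falls from 3.35 to 3.19, 2.90 and 2.39 points. The equivalent gain in sample size, 1/(1 − r²), is 1.10, 1.33 and 1.96.

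**Step 3: the cost if baseline predicts nothing.** At r = 0 the adjusted analysis loses one degree of freedom, and HADS-A power is 78.8% instead of 78.9%.

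**Step 4: do the additional models already do this?** It depends on how they are specified. Suppose baseline is entered as one more visit and the arm means are left free there. The time-by-arm contrast at the end of RT is then a comparison of change scores. With equal variances at both visits its SD is SD × √(2(1 − r)), which for HADS-A is 5.92, 5.00 and 3.87. Power at 36 per arm is 64.6%, 78.9% and 94.6%. That is below the planned t-test when r is under 0.5, and below the baseline-adjusted analysis at all three values.

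**Step 5: symptom covariate.** Nothing in the documents allows a size to be put on this, and none is claimed.

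**The case against.** The strongest reply is that nothing here is wrong. The t-test is valid under randomisation, the plan is powered for the test it names, HADS is a secondary endpoint in a feasibility pilot, and section 10.4 says the results are not meant to settle effectiveness. All of that stands, and it is why the point is only a suggestion.

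The second reply is that the gain depends on a correlation nobody has stated. That also stands. At r = 0.2, HADS-A power at 36 per arm rises only to 80.5% and the half-width falls only to 2.30 points. Section 2.1 describes anxiety peaking around week five of RT and depression rising during treatment, which gives no support for a high value. But the cost at zero correlation is negligible, so the uncertainty concerns the benefit and is no reason against adjusting.

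The third reply is that the mixed models already bring baseline in. They could: a model that constrains the arms to a common baseline mean would recover essentially the adjusted precision, and the plan does not exclude it. The change-score figures in Step 4 therefore describe one possible specification, not what the plan prescribes. What remains is that these models come second and the handling of baseline is unstated.

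Dropout adds little to the case. A mixed model uses partial records and can guard against baseline-related dropout that differs by arm, but no such dropout is documented. A simulation with about 22% missing by the same baseline-related mechanism in both arms put the null t-test difference at 0.00 to 0.01 points, so no bias is claimed.

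The symptom sentence is permissive, sits under the exploratory endpoints, and speaks of symptom presence, whereas the hypothesis concerns bother. It deserves a clarification and no more.

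**Conclusion.** The point holds as a loss of precision and incomplete pre-specification, not as bias or an arithmetic error. With the full 72 participants, leaving baseline out costs about 4 percentage points of power at r = 0.3, about 10 at r = 0.5 and 17 to 18 at r = 0.7. At 25 per arm the cost is about 4, 12 and 26 points. These figures rest on the plan's own means and SDs, on complete data, on a linear relation with baseline, and on the assumed correlations. The symptom covariate is a gap in wording with no claimed effect on the results.

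**What to change.** In section 10.3.3, make the lead analysis of each HADS subscale a mixed model on all randomised participants, with arm, visit, arm-by-visit and the baseline score of the same subscale as a covariate. Report the adjusted difference with its 95% confidence interval at the end of RT and at one month. Keep the t-test as a descriptive check.

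The same edit should name which of the two time points leads: the Synopsis and section 4.2.2 place the secondary endpoint at one month after RT, while sections 10.3.3 and 10.4 test and power it at the end of RT. Baseline adjustment works at either.

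In section 4.2.3, state that any symptom covariate is the baseline MSAS-SF value.

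The cost is a few sentences of analysis-plan wording and slightly more analysis work. All the data are already scheduled, so no visit, questionnaire or participant is added.

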10.3.4 ADHERENCE AND RETENTION ANALYSES

Given that the feasibility of recruitment, enrollment, and completion of the study are secondary objectives of this project, we will evaluate study retention. Specifically, analyses will evaluate the number of participants approached, the number consented, the number who access the REDCap Survey, and the number who complete the survey. Study personnel will attempt to contact persons who failed to complete the study to ask why they dropped out. Data gathered will be used to inform future studies and grant applications.

10.3.6 TABULATION OF INDIVIDUAL RESPONSE DATA

Individual data will be entered into REDCap using a unique study identification number.

10.3.7 EXPLORATORY ANALYSES

The study investigators will use descriptive statistics (i.e., proportions of people at each time point) to examine differences in anxiolytic use between treatment groups. At the end of RT, a chi-square or Fisher's exact test will be used to determine if there is a difference in the proportion of people using anxiolytics by treatment group.

10.4 SAMPLE SIZE

We expect that we will be able to enroll up to 72 patients who will be randomized into either control (n=36) or guided imagery intervention (n=36). Based on a published study looking at HADS scores in HNC patients receiving RT (20), we used the values for means and standard deviations (SD) from that study for our control group. We also determined that SD would be known and equal. Significance levels (alpha) are set at 0.05 for a two-sided independent-sample equal-variance t-test. For the HADS-A hypothesis, the mean score in controls at the end of RT was 6.9 (SD = 5.0). With group sample sizes of 36 and 36, we will have 80% power to reject the null hypothesis of equal means when the HADS-A score in the guided imagery group is ≤ 3.6 (a $\geq 48\%$ difference between the scores for each group at the end of RT). For the HADS-D hypothesis, the mean score in controls at the end of RT was 11.2 (SD=5.5). Group sample sizes of 36 and 36 achieve 80% power to reject the null hypothesis of equal means when HADS-D score in the guided imagery group is ≤ 7.5 (a $\geq 33\%$ difference between the scores at the end of RT). Although we can achieve reasonable power to detect clinically significant differences

between our study groups, the main goal of this study is to determine the feasibility of a larger study. As such, the results of our analyses are not meant to answer the question of the effectiveness of our intervention, but to provide preliminary data for a larger grant application.

10.5 MEASURES TO MINIMIZE BIAS

10.5.1 ENROLLMENT/ RANDOMIZATION/ MASKING PROCEDURES

The REDCap randomization tool will be used to facilitate randomization. [name] will create random allocation tables that she will either upload into the REDCap project or will provide to the REDCap Administrator to be uploaded. [name] will generate the random allocation tables according to study design specifications as determined by the statistician and investigator/s. Participants will be randomized when the research study assistant or study investigator enter a participant's REDCap record and click the "Randomize" button. Clicking this button triggers REDCap to check the allocation table and display the group to which the participant should be randomly assigned. This assignment is permanent and not editable within the participant record and, like all other activity within REDCap, is tracked and not modifiable in the audit log.

11 SOURCE DOCUMENTS AND ACCESS TO SOURCE DATA/DOCUMENTS

Appropriate research records will be maintained as necessary; however, all data collection will occur via REDCap, so it is likely any creation of source documents will be minimal.

